9.3 Study Restrictions

9.3.1 Additional Dietary Restrictions/Prohibited Medications

Prohibited medications and certain foods are not allowed in this study (Screening Period through Safety Follow-up Visit) (Table 9-1). Both ivacaftor and VX-661 are metabolized at least in part via hepatic enzymatic pathway utilizing CYP3A4, hence the need to restrict usage of known CYP3A4 inducers and inhibitors.

A nonexhaustive list of study prohibitions and cautions for food and medication will be provided in the Study Reference Manual.

Table 9-1 Study Restrictions

Restricted Medication/Food	Study Period	
	Screening Period	Treatment Period through Safety Follow-up Visit
Certain fruits and fruit juices (Grapefruit, grapefruit juice, Seville oranges, marmalade)	None allowed within 14 days before the first dose of the study drug	None allowed through the Safety Follow-up Visit
Moderate and strong CYP3A inducers	None allowed within 14 days before the first dose of the study drug	None allowed through the Safety Follow-up Visit
Moderate and strong CYP3A inhibitors (except for ciprofloxacin)	None allowed within 14 days before the first dose of the study drug	None allowed through the Safety Follow-up Visit
Commercially available CFTR modulators (e.g., Kalydeco)	None allowed within 30 days before and during Screening	None allowed through the Safety Follow-up Visit

CYP: cytochrome P450.

Note: The use of restricted medication by subjects with medical needs will be addressed on a case-by-case basis with the medical monitor.

9.4 Prior and Concomitant Medications

Information regarding all prior and concomitant medications, including the subject's CF medications, other medications, and herbal and naturopathic remedies administered from 28 days before the Screening Period through the Safety Follow-up Visit, if applicable, will be recorded in each subject's source documents. For subjects who are screened but are not subsequently randomized into the study, details of prior medication will only be documented in the subjects' source documents.

- Subjects must remain on a stable medication (and supplement) regimen for their CF from 28 days before Day 1 through the Safety Follow-up Visit. Stable medication regimen is defined as the current medication regimen for CF that subjects have been following for at least 28 days before Day 1. Subjects must not initiate long-term treatment with new medication from 28 days before Day 1 through the Safety Follow-up Visit, unless discussed and approved by the Vertex medical monitor. Guidelines for stable medication regimens for CF are as follows:
 - Subjects who are taking daily inhaled tobramycin or other chronically inhaled antibiotics should remain on that regimen throughout the study.
 - Subjects who are on inhaled cycling antibiotics should continue on their prior schedule. The timing of the first dose of study drug should be synchronized as closely as possible to the first day of inhaled cycling antibiotics in the cycle.
 - Subjects who alternate 2 different antibiotics monthly should remain on the same schedule during the study. The timing of the first dose of study drug should be synchronized as closely as possible to the first day of 1 of the inhaled alternating antibiotics.
- Subjects may receive doses of prednisone of up to 10 mg/day (chronically) or prednisone 60 mg qd for up to 5 days without prior approval of the medical monitor.

- Information about bronchodilator use during the study will be collected and documented. Subjects who are using a bronchodilator must have their spirometry assessments performed according to the guidelines provided in Section 11.6.1.
- Concomitant use of medications known to prolong the QT interval should be used with caution during the study, as the effect of VX-661 in combination with ivacaftor on the QT interval has not been evaluated in a thorough QT study. Consideration should be given to obtaining an ECG when concomitant medication known to prolong the QT interval is administered.

9.5 Removal of Subjects

Subjects may withdraw from the study at any time at their own request. Subjects may be withdrawn from study drug treatment at any time at the discretion of the investigator or Vertex for safety, behavior, noncompliance with study procedures, or administrative reasons. If a subject has been withdrawn from study drug treatment, the subject should continue to be followed, provided the subject has not withdrawn consent.

If a subject does not return for a scheduled visit, reasonable effort will be made to contact the subject. In any circumstance, reasonable effort will be made to document the subject's outcome. The investigator will inquire about the reason for withdrawal, request that the subject return all unused investigational product(s), request that the subject return for a Safety Follow-up Visit, if applicable (see Section 8.1.4), and follow up with the subject regarding any unresolved AEs.

If the subject withdraws consent, no further evaluations will be performed and no additional data will be collected. Vertex may retain and continue to use any data collected before such withdrawal of consent. Subjects who discontinue study treatment early should continue to return for study assessments as noted in Section 8.1.4.

The investigator should inquire about the reason for withdrawal of consent.

Subjects must return all unused study drug and return for all scheduled visits.

A subject will be withdrawn from study drug treatment for any of the following reasons:

- A female subject or a female partner of a male subject has a confirmed pregnancy.
- A subject's treatment is unblinded by the investigator.

A subject may be withdrawn from study drug treatment after a discussion between the investigator and the medical monitor for any of the following reasons:

- A subject develops a medical condition that requires prolonged concomitant therapy with a prohibited medication or prolonged interruption of the study drug.
- A subject develops a life-threatening AE or a serious AE (SAE) that places him/her at immediate risk, and discontinuation of study drug treatment and withdrawal from the study are deemed necessary.
- A subject is noncompliant with study requirements.

- A subject has an increase in transaminases (ALT or AST) according to evaluations and management described in Section 11.7.7.
- A subject has an increase in QTc according to evaluations and management described in Section 11.7.4.
- A subject develops a cataract or lens opacity.

Subjects who discontinue study treatment early should continue to return for assessments as noted in Section 8.1.4.

9.6 Replacement of Subjects

Subjects who withdraw or are withdrawn for nonsafety reasons during the study drug treatment period may be replaced at Vertex's discretion.

10 STUDY DRUG ADMINISTRATION AND MANAGEMENT

Study drug refers to VX-661/ivacaftor, ivacaftor, and their matching placebos.

10.1 Preparation and Dispensing

Study drug may be dispensed only under the supervision of the investigator or an authorized designee and only for administration to the study subjects.

10.2 Administration

Study drug tablets will be administered orally. Subjects will receive the same number of tablets each day to maintain the blind. Refer to Table 10-1.

Table 10-1 Study Drug Administration - Treatment Period

Treatment Arm	Time	Drug(s) and Dose(s) Administered Route of Administration
VX-661/ivacaftor	AM	VX-661 100-mg/IVA 150-mg fixed-dose tablet oral
	PM	IVA 150-mg tablet oral
Placebo	AM	VX-661/IVA matching placebo tablet oral
	PM	IVA matching placebo tablet oral

AM: morning; IVA: ivacaftor; PM: evening.

Study drug should be administered within 30 minutes of starting a meal with fat-containing food, such as a standard "CF" high-fat, high-calorie meal or snack, according to the following guidelines:

1. Throughout the Treatment Period, study drugs will be administered after the start and before the end of a meal. It is recommended that the duration of each meal associated with study drug intake (i.e., breakfast and dinner/snack, as applicable) should not exceed 30 minutes.
2. Study drug should be administered q12h (\pm 2 hours). For each subject, all doses (morning and evening) of study drugs will be taken at approximately the same time each day. For example, the morning dose could be taken at 08:00 every morning and the evening dose could be taken at 20:00 every evening throughout the study.
3. At the Day 1 Visit, all subjects will be observed for 6 hours after the morning dose of the study drug.
4. The date, amount taken, and time of study drug administration, including whether food was taken with each dose, will be recorded for 2 days before PK sample collection and on the days of PK sample collection.
5. On days of scheduled visits, the morning dose of study drug will be administered at the site after predose assessments have been completed. The meal or snack will be provided by the site for the morning dose of study drug.
6. If a subject's scheduled visit is to occur in the afternoon, the following guidelines must be used:
 - If the dose in the clinic will be within 6 hours of the subject's scheduled morning dose, the subject should withhold their morning dose of study drug and the morning dose will be administered in the clinic.
 - If the dose in the clinic will be more than 6 hours after the subject's scheduled morning dose, the subject should take the morning dose at home and the evening dose will be administered in the clinic. In this event, all assessments will be collected relative to the evening dose.
7. For visits after the Day 1 Visit, subjects will be instructed to bring all used and unused study drug to the site; study drug will be dispensed at each visit, as appropriate.
8. At the Week 24 Visit, the morning dose of study drug will NOT be administered. The last dose of study drug will be the evening dose administered the day before the Week 24 Visit.

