ⁱ All subjects will have an ophthalmologic examination conducted by a licensed ophthalmologist at Week 24. This exam may be completed within 4 weeks before the Week 24 Visit, but must be completed by the end of the Week 24 Visit. Subjects <18 years of age at the Screening Visit who complete an ophthalmologic exam at the ETT Visit will not be required to complete another ophthalmologic exam at the Week 24 Visit.

^j Subjects <18 years of age at the Screening Visit who discontinue treatment after receiving at least 1 dose of study drug treatment, and subjects <18 years of age at the screening who complete treatment but do not enroll in a separate extension study of VX-661/ivacaftor within 28 days of the last dose of study drug will have an ophthalmologic exam conducted by a licensed ophthalmologist at the Safety Follow-up Visit or ETT Visit (see Section 11.7.8). The exam may be completed at either the ETT or Safety Follow-up Visit, but must be completed by the date of the Safety Follow-up Visit. Subjects who complete an ophthalmologic exam at the ETT Visit or Week 24 Visit will not be required to complete another ophthalmologic exam at a subsequent visit.

^k Subjects will have a complete physical examination (as defined in Section 11.7.3) as noted. Symptom-targeted physical examinations will occur at any time during the study if triggered by AEs or if deemed necessary by the investigator.

^l Pregnancy tests will be performed for all female subjects of childbearing potential. A urine β -hCG test will be performed on Day 1 (before first dose of study drug) and every 4 weeks thereafter.

^m All standard 12-lead ECGs will be performed before dosing and after the subject has been supine for at least 5 minutes. At the Days 1 and 15 Visits, ECGs will be collected before dosing and at 1.5, 3, 4, and 6 hours after the morning dose; the 4-hour postdose ECG will be collected before the 4-hour postdose spirometry assessment. ECGs collected on Day 1 before dosing will be performed in triplicate. If study drug is not administered on the day of the visit (i.e., because of study drug interruption or permanent discontinuation of study drug), only 1 ECG will be collected.

ⁿ Vital signs and pulse oximetry will be collected before dosing and after the subject has been at rest (seated or supine) for at least 5 minutes.

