^o At all visits, spirometry must be performed for all subjects before dosing and should be performed prebronchodilator (Section 11.6.1). At Day 1 and Day 15, subjects <18 years of age at the Screening Visit will have additional spirometry performed at 2 and 4 hours postdose. If more than 1 spirometry assessment is required at a visit, bronchodilators should be withheld until the last scheduled spirometry assessment is completed.

^p Sweat chloride collection will occur approximately 1 hour before the PK sample collection and before the morning dose of the study drugs. At each time point, 2 samples will be collected, 1 from each arm (left and right). Collection of sweat chloride will not overlap with any other study assessments.

Table 3-2 Treatment Period and Safety Follow-up Visit Assessments – VX14-661-106

Event/Assessment ^a	Day 1	Day 15 (± 3 days)	Week 4 (± 5 days)	Week 8 (± 5 days)	Week 12 (± 5 days)	Week 16 (± 5 days)	Week 20 (± 5 days)	Week 24 (± 5 days)	ETT Visit ^b	Safety Follow-up Visit 28 (± 7) days After the last dose of study drug (if applicable) ^c
Serum chemistry	X ^a	X	X	X	X	X		X	X	X
Lipid panel ^r	X				X			X	X	
Vitamin levels	X				X			X	X	
PK sampling ^s	X				X	X			X	X
[REDACTED]										
[REDACTED]										
[REDACTED]										
[REDACTED]										
[REDACTED]										
Other events related to outcome ^u	X	X	X	X	X	X	X	X	X	
Randomization ^v	X									
Meal(s) or snack(s) at site ^w	X	X	X	X	X	X				
Study drug dosing ^x	Day 1 through Week 24									
Study drug count		X	X	X	X	X		X	X	

^a Blood samples will be collected before the first dose of study drug.

^r Blood samples will be collected for the lipid panel following at least a 4-hour fast.

^s PK samples will be collected on Day 1 at predose; at Week 12 (predose, 0.5, 3, and 6 hours after the morning dose); and at Week 16 (predose, 2, 4, and 8 hours after the morning dose). At the Safety Follow-up Visit and ETT Visit, a single blood sample for PK will be collected. If study drug is not administered on the visits of Weeks 12 and 16 (i.e., study drug interruption or permanent discontinuation of study drug), only 1 PK blood sample will be collected at each of these 2 visits.

[REDACTED]

^u Other events related to outcome include assessments relating to pulmonary exacerbations, administration of antibiotic therapy for sinopulmonary signs or symptoms, and hospitalizations (Section 11.6.12).

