^v Randomization must occur after all inclusion and exclusion criteria are met and before the first dose of study drug. Randomization will be done through IWRS. Randomization may occur on Day -1.

^w Fat-containing food such as a standard "CF" high-fat, high-calorie meal or snack will be provided at the site to subjects after all predose assessments have occurred.

^x The study drug should be administered every 12 hours (± 2 hours) within 30 minutes of starting a meal with fat-containing food such as a standard "CF" high-fat, high-calorie meal or snack. On days of scheduled visits, the morning dose of study drug will be administered at the site after predose assessments have been completed. The final dose of study drug will be administered the evening before the Week 24 Visit.

Table 3-2 Treatment Period and Safety Follow-up Visit Assessments – VX14-661-106

Event/Assessment ^a	Day 1	Day 15 (± 3 days)	Week 4 (± 5 days)	Week 8 (± 5 days)	Week 12 (± 5 days)	Week 16 (± 5 days)	Week 20 (± 5 days)	Week 24 (± 5 days)	ETT Visit ^b	Safety Follow-up Visit 28 (± 7) days After the last dose of study drug (if applicable) ^c
Concomitant medications ^y	X	X	X	X	X	X	X	X	X	X
Concomitant treatments and procedures	X	X	X	X	X	X	X	X	X	X
AEs and SAEs ^z	Continuous from signing of the ICF and Assent (where applicable) through the Safety Follow-up Visit									

AE: adverse event; β-hCG: beta-human chorionic gonadotropin; CF: cystic fibrosis; CFQ-R: CF Questionnaire–Revised; [REDACTED]; ECG: electrocardiogram; ETT: Early Treatment Termination; IWRS: interactive web response system; PE: physical examination; PK: pharmacokinetic; [REDACTED]; SAE: serious adverse event; [REDACTED].

^y All concomitant medications are collected through the Safety Follow-up Visit for all subjects. For subjects who discontinue treatment and are followed for certain efficacy assessments after the ETT Visit (see Section 8.1.4), concomitant antibiotic therapy for ‘sinopulmonary signs and symptoms’ are collected through the Week 24 Visit, as described in Section 11.6.12.1.

^z SAEs that occur after the Safety Follow-Up Visit and are considered related to study drug(s) will be reported to Vertex GPS **within 24 hours** as described in Section 13.1.2.2.

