8.1.2 Treatment Period (Day 1 Through Week 24)

The Treatment Period will last approximately 24 weeks. Subjects will be randomized to 1 of 2 treatment arms: 1 combination treatment arm and 1 placebo arm. The dosing regimen for each treatment arm is shown in Figure 8-1 and is as follows:

- VX-661/ivacaftor: 100-mg VX-661/150-mg ivacaftor fixed-dose combination (light yellow) film-coated tablet for oral administration (morning dose); 150-mg ivacaftor (light blue) film-coated tablet for oral administration (evening dose)
- Placebo: 0-mg film-coated matching placebo tablets for oral administration (1 light yellow for morning dose and 1 light blue for evening dose)

The first dose of the study drug will be administered after randomization on Day 1. Dosing details are given in Section 10.2.

Study visits during the Treatment Period will occur as shown in Table 3-2. Subjects will be outpatients during the Treatment Period. All visits should occur within the windows specified.

Subjects who prematurely discontinue study drug treatment will remain in the study from the time of discontinuation of study drug treatment through the Week 24 Visit and complete assessments for all study visits, as described in Section 8.1.4.

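### For late clinic doses, Protocol 10.2 item 6 times all assessments to the ivacaftor-only evening tablet, against Table 3-2, so Day 15 post-dose ECGs and adolescent spirometry fall more than 7.5 h after VX-661

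*Protocol*

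**What the plan says.** Protocol Table 10-1 puts VX-661 in the morning fixed-dose tablet only. The active evening dose is "IVA 150-mg tablet oral".

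The default in Section 10.2 item 5 and Table 3-2 footnote x is that the morning dose is given at the site on visit days. The serial assessments are set as follows:

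- **ECG, Days 1 and 15 (footnote m):** "ECGs will be collected before dosing and at 1.5, 3, 4, and 6 hours after the morning dose".
- **PK, Week 12 (footnote s):** "at Week 12 (predose, 0.5, 3, and 6 hours after the morning dose". The Week 16 samples, before dosing and 2, 4 and 8 h later, use the same reference tablet.
- **Adolescent spirometry, Days 1 and 15 (footnote o):** 2 and 4 h after dosing, without naming the tablet.

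Section 10.2 item 6 gives mandatory rules for afternoon visits. If the clinic dose falls within 6 h of the scheduled morning dose, the morning tablet is held back and given in clinic. If it would fall later than that, the subject takes the morning tablet at home and the evening tablet in clinic, and then: "In this event, all assessments will be collected relative to the evening dose". No visit or assessment is exempt, and the footnotes do not refer to item 6.

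The SAP repeats the morning-dose reference for ECGs (11.2 and the schedule in 11.1). It summarises ECGs by scheduled time point (8.4.3) and adolescent spirometry at 2 and 4 h (8.4.6). It has no rule for records timed to the evening tablet.

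**The concern.** In the second branch of item 6 the clock starts at a tablet that contains no VX-661. The Day 15 records then carry the same time labels as those taken after the combination tablet, but they miss the first hours after VX-661. The Day 15 predose value is also taken after that day's VX-661 dose, so both ends of the change from predose in SAP 8.4.6 are displaced.

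Day 15 is the only visit after repeated dosing with serial post-dose ECGs and adolescent post-dose spirometry. Protocol 8.2.4 says a regulatory authority asked for that spirometry. Protocol 9.4 says the combination's effect on QT has not been studied in a thorough QT trial. These are the summaries that should describe the hours after the combination tablet.

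The stated rules may not let anyone pick out the affected records. Under item 4, dose times "will be recorded for 2 days before PK sample collection and on the days of PK sample collection", and Day 15 has no PK sampling.

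The branch also sits badly with the dosing interval. Its trigger is more than 6 h, while item 2 and footnote x require 12 h ± 2 h between doses.

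**Working it through.** The plan states no figure to reproduce here. The check is a comparison of rules plus simple addition.

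**Inputs**

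- Gap *g* from the home morning tablet to the clinic evening tablet: more than 6 h under item 6 as written, or 12 ± 2 = 10 to 14 h if the dosing window is also kept.
- Nominal times *t* after the clinic tablet: footnotes m, o and s.
- Assumption: the home dose is taken at its scheduled time.

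**Formula:** hours since VX-661 = *g* + *t*.

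| Assessment | *t* (h) | *g* > 6 h | *g* = 10 to 14 h |
|---|---|---|---|
| Day 15 ECG | 1.5, 3, 4, 6 | >7.5, >9, >10, >12 | 11.5–15.5, 13–17, 14–18, 16–20 |
| Day 15 spirometry, age <18 | 2, 4 | >8, >10 | 12–16, 14–18 |
| Week 12 PK | 0.5, 3, 6 | >6.5, >9, >12 | 10.5–14.5, 13–17, 16–20 |
| Week 16 PK | 2, 4, 8 | >8, >10, >14 | 12–16, 14–18, 18–22 |

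For example, the first ECG is at 6 + 1.5 = 7.5 h as a lower bound, and the last in-window ECG is at 14 + 6 = 20 h. Had the morning tablet been given in clinic, each value would equal *t*.

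**Clock times, using the protocol's own 08:00/20:00 example**

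1. The branch applies to a clinic dose after 08:00 + 6 h = 14:00.
2. The dosing window allows the evening tablet from 08:00 + 10 h = 18:00 to 08:00 + 14 h = 22:00.
3. A clinic evening dose between 14:00 and 18:00 therefore meets item 6 but is only 6 to 10 h after the morning dose, outside the window.
4. An in-window dose puts the 6-h ECG at 00:00 to 04:00, in subjects who are "outpatients during the Treatment Period".
5. If the series is to end by 22:00 (an illustrative limit), the clinic dose must be given by 22:00 − 6 h = 16:00. That is 8 h after the morning dose, below the 10-h minimum.

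At Day 15 the branch is therefore either outside the dosing window or impractical for outpatients.

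**What is not affected**

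- *First branch of item 6.* The combination tablet is given in clinic, at most 6 h late, which Section 10.6 tolerates.
- *Day 1.* There is no earlier home dose, and item 3 requires observation after the morning dose.
- *Footnote o.* It names no tablet, so it is not literally contradicted. Spirometry simply follows whichever tablet is given in clinic.
- *Sample size and primary analysis.* Neither uses these times.

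**The case against.** The strongest reply is that item 6 is a specific exception to the default in item 5, so nothing is contradicted and only a cross-reference is missing. Even as an exception, it yields Day 15 records that share a label with correctly timed ones but describe a different interval after VX-661. The SAP then summarises them together.

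A second reply is that the clock times above make the branch unlikely at exactly these visits, so few records would be affected. That largely stands. The documents give no count and the share is probably small, which is why the priority is low.

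Third, item 6 does not waive the 12 h ± 2 h rule, and its 6-h test only decides whether the morning dose can still be held for clinic. But the item covers afternoon visits, and on the 08:00 example every clinic evening dose between 14:00 and 18:00 breaks that window. The text gives sites no way to reconcile the two.

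Fourth, the case report form may capture Day 15 dose times, and staff need the dose time to run a timed series. That is fair, because the form is not in the documents. The point is only that the protocol's stated recording rule does not require it.

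Fifth, no consequence for a result is shown. This also stands. The time course of any VX-661 effect is not given, so no dilution can be claimed. Safety output is descriptive, and PK samples remain usable through recorded dose times and population modelling, although they miss the early VX-661 phase.

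**Conclusion.** The concern holds, at low priority. As written, the second branch of item 6 cannot be followed together with footnotes m and s. It puts Day 15 post-dose ECGs more than 7.5 h, and adolescent post-dose spirometry more than 8 h, after VX-661. If the dosing window is kept, the ranges are 11.5 to 20 h and 12 to 18 h. The branch also admits a dosing gap of 6 to 10 h, outside 12 h ± 2 h.

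The offsets rest on the home dose being taken on schedule. The clock times rest on the protocol's 08:00/20:00 example. How many visits use the branch, and whether the displaced timing hides any effect, cannot be determined from the documents. The wording conflict and the arithmetic are certain; the practical effect is probably small.

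**What to change.** - **Protocol 10.2 item 6:** exempt Day 15, Week 12 and Week 16 from the second branch. Book these visits so that serial assessments follow the fixed-dose morning tablet given in clinic, and cross-refer to footnotes m, o and s.
- **Other visits:** state that an evening dose given in clinic must still be at least 10 h after the morning dose.
- **Data collection:** record at Day 15 which tablet was taken and when.
- **SAP 8.4.3 and 8.4.6:** summarise the Day 15 post-dose records that follow the fixed-dose tablet (or its matching placebo), and list any others.

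The cost is one protocol clarification, one added data entry at Day 15 and one sentence in each of two SAP sections. Sites lose some scheduling freedom at three visits, and any mistimed Day 15 records move from tables to listings.
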